2.2.3. Pharmacokinetic Variable(s)

For all subjects, blood samples will be collected twice during the trial to measure for dasiglucagon levels at steady-state on Day 6 and Day 25. PK Sampling for drug exposure at Visit 5 is only applicable for patients with a body weight of ≥ 4 kg.

3. Overall Study Design and Plan

This is a combined phase 2 and 3, randomized, multinational trial to evaluate the efficacy and safety of individually titrated dasiglucagon in children ≥ 7 days and <1 year of age who have been diagnosed with CHI, comprising 2 parts, a crossover (2 periods, 48 hours each), double-blind, placebo-controlled Part 1, and an open-label, single-arm Part 2 of 21 days.

After screening, eligible patients will complete a minimum 24-hour run-in period to confirm the IV glucose randomization requirement (≥ 10 mg/kg/min). All non-nutritional carbohydrates and carbohydrate fortification of feeds are prohibited during this 24-hour run-in period. After the run-in period, patients will be randomly assigned in a double-blind fashion to receive dasiglucagon or placebo for 48 hours, after which they will be crossed over to the other trial treatment for an additional 48 hours. At the time of crossover, the trial drug will be initiated from the starting dose of 10 μ g/hr, and IV GIR will be set to the rate obtained at the end of the run-in period which corresponds to the last value obtained before randomization.

and titrated accordingly.

[figure not shown]
There will be no washout between the 2 periods in Part 1 to limit the length of time in which patients are reliant on IV GIR as their only means of preventing/treating hypoglycemia.

During Part 1, the trial drug and IV GIR should be adjusted according to the protocol-specified algorithm. Non-nutritional carbohydrates and/or carbohydrate fortification of feeds during Part 1 is only allowed when the maximum tolerable volume and concentration of IV glucose for the patient is reached, and should be limited to the minimum needed to ensure the patient's safety. All feedings (administered as parenteral nutrition, by nasogastric [NG] tube, gastrostomy, or normal route), will be recorded during this period.

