6.1.7. Derived Variables

- **Day 1** = First day of Treatment (Placebo or Dasiglucagon) during Part 1. Study day will be calculated with respect to Day 1.
- **Treatment period**

As primary and secondary endpoint assessments are not performed at planned visits but continuously during the study, we have to define treatment periods. Those will then be used to assign a treatment period to an evaluation.

Treatment periods created will be:

- Part 1 – Treatment period 1: First 48-hours treatment period
- Part 1 – Treatment period 2: Second 48-hours treatment period
- Part 1 – Last 12 hours per treatment period
- Part 2

[Table 4](#) describes the derivation for each of those treatment periods.

Table 4: Derivation of Treatment Periods

Part	Time Point	Treatment Period (TP)	Start date	End date
Part 1		TP1	Day 1	Last exposure treatment period 1
		TP2	First exposure treatment period 2	Last exposure treatment period 2
Part 1	Last 12-hour/24-hour per TP	TP1	End date minus 12 hours/24 hours	Last exposure treatment period 1
		TP2	End date minus 12 hours/24 hours	Last exposure treatment period 2
Part 2			Day 5 first exposure	End of study exposure

Abbreviations: TP1 = treatment Part 1, TP2 = treatment Part 2

- **Study Week:** to be defined for Part 2 only
 - A 7-day period derived for displays of events related to CGM and/or SMPG results, gastric carbohydrate administrations, health care outcomes, and other assessments that may occur between clinic visits where a defined study week is needed.

The study weeks will be derived as follows:

Table 5: Study weeks

Study Week	Start	End
Week 1	Day 5 first exposure	Start + 167 hours 59 minutes
Week 2	End date week 1 + 1 minute	Start + 167 hours 59 minutes
Week 3	End date week 2 + 1 minute	Start + 167 hours 59 minutes

- **Change from baseline** = value at current time point – value at baseline.
- **TEAE** = an AE with an onset at the time of or following the start of treatment with the trial drug (dasiglucagon or placebo) through the Follow-up visit or Early Termination visit, whichever occurs first.
- **Weighted Mean IV GIR:** AUC will be calculated using linear trapezoidal method and divided by the length of the time period in minutes. The weighted mean IV GIR endpoint is expressed as glucose in mg/kg/min. This will be calculated over last 12 hours of each treatment period and over last 48 hours of each treatment period during Part 1.

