where UL is the upper limit for the hypoglycemia definition (70 mg/dL or 54 mg/dL); k is the k^{th} time point that glucose is measured using CGM; PG_k is the PG value in mg/dL on the k^{th} time point; and X is the end time point of the 3-week treatment period (Weeks 2-4). When $k = 0$, t_k is set to 0 and PG_k is the PG value corresponding to the start of the 3-week treatment period. Only PG values less than UL will be included in the calculation. If $PG \geq UL$ at the k^{th} time point and $PG < UL$ at the $k^{\text{th}}+1$ time point, then the extent of hypoglycemia for that interval will be determined as follows:

1. Estimate time point on x-axis where $PG = UL - 0.01$, as if a straight line were drawn between time points by using the following formula:

$$\hat{k} = \frac{(UL - 0.01) - b}{m}$$

Where b = y-intercept of line created by the coordinates (k^{th} time point, PG_k) and ($k^{\text{th}}+1$ time point, PG_{k+1}) and m = slope of that line.

2. Substituting PG_k with UL and t_k with $t_{\hat{k}}$, the formula for the estimated interval below UL is as follows:

$$\frac{(UL - UL) + (UL - PG_{k+1})}{2} \times (t_{k+1} - t_{\hat{k}})$$

Similar methodology would be utilized if $PG < UL$ at the k^{th} time point and $PG \geq UL$ at the $k^{\text{th}}+1$ time point, with the estimate of the time point where PG crosses the UL threshhold being estimated for $t_{\hat{k}+1}$.

If the time period between two timepoints is greater than 1 hour then no interpolation will be performed and no area will be calculated over this timeperiod.

If PG results from the k^{th} time point are missing, then $k-1$ scores will be used and the weight will be $t_{k+1}-t_{k-1}$.

The extent of hypoglycemia calculated as above will then be divided by the total duration of CGM assessments calculating as summing all $t_{k+1}-t_k$ duration used in previous formulae. Time points for which $PG>UL$ will be included in the total duration. This variable will then be used the endpoint evaluation.

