8.3.1. Primary Analyses for Secondary Endpoints

Part 1 (Day 1 to 4, for each 48-hour treatment period)

- Weighted Mean IV GIR for each 48-hour treatment period during Part 1 (dasiglucagon or placebo administration). This endpoint will be analyzed using the same mixed-model regression approach as the one used for primary endpoint and removing IV GIR data that are not valid for site 101. No sensitivity analysis on this endpoint.

- Weighted Mean IV GIR below 10 mg/kg/min in the last 12 hours of each treatment period during Part 1 (yes/no) (dasiglucagon or placebo administration). For this analysis a generalized estimating equation (GEE) method with logit link function will be used using below program and removing IV GIR data that are not valid for site 101.

```
PROC GENMOD;  
  CLASS PATIENT PERIOD TRT;  
  MODEL OUTCOME= PERIOD TRT / LINK=LOGIT DIST=BINOMIAL ;  
  REPEATED SUBJECT=PATIENT/ WITHIN=PERIOD TYPE=CS;  
  LSMEANS TRT / ILINK CL EXP DIFF;  
  ESTIMATE "DASIGLUCAGON versus PLACEBO" TRT 1 -1 ;  
RUN;
```

Part 2 (Day 5 to 25, assessed from the start of treatment in part 2)

If patient needs a pancreatectomy, this will occur only during the Part 2 of the study. If pancreatectomy was done before randomization, it will not be taken into account. Only patients with pancreatectomy during the study will have censored values.

The evaluation of the Part 2 endpoints will then be impacted by pancreatectomy. To be able to assess only treatment effect as primary analysis the following rules will be applied:

- SMPG-detected episode, Carbohydrates administrated, CGM-detected episode, CGM percent time endpoint and extent of hypoglycemia will be set to missing after pancreatectomy (whatever percentage of pancreatectomy).
- Time to complete weaning off IV GIR and time to actual hospital discharge will be censored at time of pancreatectomy (whatever percentage of pancreatectomy).

Following endpoints will be described by week and over the three weeks period.

- Time to complete weaning off IV GIR. Only patient without complete weaning off IV GIR at start of Part 2 will be included in this analysis. Kaplan-Meier estimates will be given for each of the three weeks treatment period.
- Rate of SMPG-detected hypoglycemia episode, defined as number of hypoglycemic events (PG <70 mg/dL or 3.9 mmol/L).
- Rate SMPG-detected Clinically significant hypoglycemia episode, defined as number of events <54 mg/dL (3.0 mmol/L).

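### The extent-of-hypoglycemia derivation labels its window Weeks 2-4, but Part 2 has only Weeks 1-3; if the label is followed, Week 1 is lost.

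*SAP*

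**What the plan says.** The extent of hypoglycemia is defined in SAP 6.1.7 (Derived Variables) as a trapezoidal area between the threshold and the CGM curve, divided by the total CGM duration.

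- **End of the window.** X "is the end time point of the 3-week treatment period (Weeks 2-4"; the bracket closes there.
- **Start of the window.** At k = 0, the glucose value used "is the PG value corresponding to the start of the 3-week treatment period". No week numbers are attached to this statement.
- **Study weeks.** Earlier in the same section, study weeks are "to be defined for Part 2 only", and their stated uses include CGM displays. In Table 5, Week 1 starts at "Day 5 first exposure" and every week ends at "Start + 167 hours 59 minutes". The last row, Week 3, starts at "End date week 2 + 1 minute".
- **Length of Part 2.** SAP Section 3 describes an "open-label, single-arm Part 2 of 21 days".
- **Analysis.** SAP 8.3.1 lists both extent endpoints (thresholds 70 and 54 mg/dL) under "Part 2 (Day 5 to 25, assessed from the start of treatment in part 2", again in a bracketed heading. It asks for each listed endpoint by week and across the three weeks. SAP 2.2.2 and Protocol 7.2.3 give the same Day 5 to 25 window.

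**The concern.** The bracketed label names a week that Table 5 does not define and leaves out one that it does. It is also the only place in the formula where the 3-week period is identified by week number, so a programmer who selects CGM records with the Table 5 week flags could reasonably take it as the selection rule. The result would be Weeks 2 and 3 only.

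Week 1 is the week most likely to differ from the others. Under SAP 3.4, every patient restarts dasiglucagon at 10 µg/hr in Part 2, with IV glucose set back to the end-of-run-in rate. The definitions of CGM percent time and CGM-detected episodes in SAP 6.1.7 carry no Weeks 2-4 label. Two CGM endpoints could therefore end up on a different window from the rest of the CGM results in the same tables.

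**Working it through.** **Inputs.** Table 5 (anchor, week length, number of weeks); SAP Section 3 (Part 2 lasts 21 days); SAP 8.3.1 (Day 5 to 25); SAP 6.1.7 (label Weeks 2-4, division by CGM duration).

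**Step 1: weeks on the Table 5 anchor.** Each week runs 167 h 59 min and the next starts 1 minute later, so week w starts at 168 × (w − 1) hours. Days are counted with first Part 2 exposure on Day 5.

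| Week | Hours from first Part 2 exposure | Study days |
|---|---|---|
| 1 | 0 to 167 h 59 min | 5-11 |
| 2 | 168 to 335 h 59 min | 12-18 |
| 3 | 336 to 503 h 59 min | 19-25 |
| 4 (not in Table 5) | 504 to 671 h 59 min | 26-32 |

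Weeks 1-3 span 3 × 168 = 504 h, and 504 / 24 = 21 days. Days 5 to 25 inclusive are 25 − 5 + 1 = 21 days. Weeks 1-3 therefore reproduce both the stated length of Part 2 and the stated assessment window.

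**Step 2: try to reproduce the label.**

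- *Weeks 2-4 on the Table 5 anchor* are Days 12-32. They share 14 of the 21 days with Part 2, omit Days 5-11 (7/21 = 33%) and add Days 26-32, beyond the planned Day 25. With only the flags that Table 5 creates, what remains is Weeks 2 and 3.
- *Weeks 2-4 counted from Day 1* are Days 8-28. They share 18 of 21 days, omit Days 5-7 and add Days 26-28.
- *Start at first Part 2 exposure, end of Week 4 as the end point* gives 4 × 168 = 672 h, or 28 days, which is not a 3-week period.

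None of these gives the 21 days of Part 2.

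**Step 3: effect on the endpoint.** The area is divided by CGM duration, so the result is a time average. Let a1, a2 and a3 be the weekly averages and assume equal CGM wear in each week.

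- Over Weeks 1-3: (a1 + a2 + a3) / 3
- Over Weeks 2-3: (a2 + a3) / 2
- Difference, first minus second: [a1 − (a2 + a3) / 2] / 3

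The documents give no weekly values, so these are assumed figures in arbitrary units:

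| a1, a2, a3 | Weeks 1-3 | Weeks 2-3 |
|---|---|---|
| 1, 1, 1 | 1.00 | 1.00 |
| 2, 1, 1 | 1.33 | 1.00 |
| 3, 1, 1 | 1.67 | 1.00 |
| 1, 2, 2 | 1.67 | 2.00 |

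The summary can move in either direction, and does not move at all if Week 1 resembles the later weeks.

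**The case against.** A reader might infer that the formula, as written, excludes the first week of open-label treatment. The documents do not support that. The sentence carrying the label also calls the window a 3-week treatment period, and the only such period in the trial is the 21-day Part 2. The next sentence starts the integration at the start of that period, without a week label; the bracket qualifies X, the end point. Reducing the label to Weeks 2 and 3 keeps half of it and contradicts the stated duration. SAP 8.3.1 also asks for by-week results from Day 5, which requires a Week 1 value. All of this stands: the text contradicts itself and does not instruct anyone to drop Week 1.

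A reader might also take the label for a deliberate later window that avoids re-titration. SAP Section 10 lists the changes from the planned analysis and includes no such change, and SAP 6.1.7 offers no rationale for one.

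It is also fair to say that 33% measures calendar time under one reading, not a bias in the endpoint, and that the consequences are small. SAP 6.1.3 and 8.3 plan no inference for Part 2 endpoints.

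What the objection does not remove is the label itself. It sits in an operative derivation, cannot be executed with the weeks that the SAP defines, and leaves the programmer to decide which statement governs.

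**Conclusion.** The point holds as an internal inconsistency. The Weeks 2-4 label conflicts with Table 5 and with SAP 8.3.1; only Weeks 1-3 fit the stated 21 days.

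The loss of Week 1 is conditional: it occurs if a programmer lets the label override the surrounding text and uses the Table 5 flags. In that case 7 of 21 days leave the overall value of two descriptive secondary endpoints. The numerical shift depends on how far Week 1 differs from Weeks 2-3; under equal wear it is one third of that difference. The documents do not show whether such a difference exists.

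The primary endpoint, the key secondary endpoint, the testing hierarchy and the power all rest on Part 1 and are unaffected. This is a minor correction, worth making because a pre-specified derivation should allow only one reading.

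**What to change.** In the extent-of-hypoglycemia definition in SAP 6.1.7, replace the bracketed Weeks 2-4 with: Weeks 1-3 of Part 2, from first exposure on Day 5. State that t = 0 is first Part 2 exposure for the overall value. Add that each weekly value is computed from the CGM readings within that week's own Table 5 boundaries, not over the three-week window. The sum uses only differences between successive times, so the placement of t = 0 matters solely through which readings are included.

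The cost is one phrase and one clarifying sentence, plus a check that any program already written selects Weeks 1-3. No new data, no change to trial conduct and no change to any other endpoint are needed.

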6.1.8. Data Adjustments/Handling/Conventions

All collected data will be presented in listings. Some data not subject to analysis according to this plan will not appear in any tables or graphs but will be included only in the data listings.

All *P* values will be displayed in four decimals and rounded using standard scientific notation (eg, 0.XXXX). If a *P* value less than 0.0001 occurs it will be shown in tables as <0.0001.

Adverse events (AE) will be coded using the MedDRA version 21.1 thesaurus.

A treatment-related AE is any AE with a relationship to the study drug of possible or probable.

If partial medication/AE dates occur, the convention for replacing missing dates for the purposes of calculating derived variables is as follows:

For partial medication/AE start dates:

- If the year is unknown, then do not impute the date but assign a missing value.
- If the month is unknown, then:
 - If the year matches the year of first dose date and the end date (if present) is after first dose date, or medication is ongoing, then impute as the month and day of the first dose date. If this produces a date after the medication end date, assign 01 January.
 - Otherwise, assign 01 January.
- If the day is unknown, then:
 - If the month and year match the month and year of the first dose date, then impute as the day of the first dose date. If this produces a date after the medication end date, assign 01.
 - Otherwise, assign 01.

For partial medication/AE end dates:

- If the year is unknown, then do not impute the date but assign as missing value.
- If the month is unknown, then assign December.
- If the day is unknown, then assign the last day of the month.

7. Study Patients/Subjects and Demographics

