After Part 1, patients will continue in open-label Part 2 to receive dasiglucagon for 21 days. Additional CHI treatments can be introduced during Part 2 if needed, if up-titration of dasiglucagon is not possible because of undesirable side effects or if the maximum dose level (70 µg/hr) has been reached. Gradual transfer from IV glucose to oral and gastric carbohydrates should be initiated in Part 2, enabling weaning of IV glucose and hospital discharge. Patients will continue to be hospitalized until IV GIR is weaned off; however, as soon as local site criteria for discharge are met, patients can be discharged to continue the treatment period at home. Planned visits can be converted to telephone visits if appropriate, at the investigator's discretion. On Day 25, the End of Treatment Visit will take place, and based on the investigator's confirmation of continued positive benefit-risk balance, patients will be offered the opportunity to participate in the long-term extension trial (Trial ZP4207-17106) to continue dasiglucagon treatment. Patients who do not enter the long-term extension trial will have a Follow-up Visit 28 days after their last dose of trial drug. [Figure 1](#) describes the study design.

No Interim Analysis is planned.

Figure 1

Abbreviations: Min = minimum

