3.5. Method of Assigning Subjects to Treatment Groups

For Part 1, patients will be randomly assigned 1:1 in a double-blind fashion to 1 of 2 sequences:

1. Dasiglucagon 4 mg/mL for 48 hours, followed by placebo for dasiglucagon for 48 hours, or

2. Placebo for dasiglucagon for 48 hours, followed by dasiglucagon 4 mg/mL for 48 hours

Randomization will be performed using a block randomization scheme stratified by region (US/non-US). The randomization scheme will be generated prior to the initiation of the trial by an independent statistician/programmer who will not be a member of the trial team; investigators will not be aware of the block size of the randomization scheme.

Patients will be randomly assigned to a trial treatment sequence using an IWRS that has been validated for the intended use under the International Society of Pharmaceutical Engineers Good automated manufacturing practice guidelines, 21CFR Part 11 (FDA regulation for Electronic Records and Electronic Signatures), and the ICH Guidance E6 for Industry on Good Clinical Practice.

After completing Part 1, patients will continue in Part 2 to receive active treatment for a maximum of 21 days.

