9.1. Adverse Events

An AE is any untoward medical occurrence in a clinical trial patient administered a medicinal (investigational or non-investigational) product and which does not necessarily have a causal relationship with this treatment. An AE can therefore be any unfavorable and unintended sign (including an abnormal laboratory finding), symptom, or disease temporally associated with the use of a product, whether or not related to the product. A treatment-emergent AE (TEAE) is defined as an AE with an onset at the time of or following the start of treatment with the trial drug (Dasiglucagon or Placebo) through the Follow-up Visit or Early Termination Visit, whichever occurs first. An AE will be assigned to the treatment period the AE started.

The causal relationship of the AE to the study drug is determined by the investigator as Not Related, Unlikely, Possible, and Probable. These will be mapped to Unrelated (*Not Related* or *Unlikely*) and Related (*Possible* or *Probable*) for summarization purposes. Any missing relationship will be mapped to “Related”.

Adverse event severity grades are reported as mild, moderate, or severe.

Each patient will be counted only once within each summation level system organ class (SOC) and preferred term (PT). The summary will be presented in descending order of frequency of SOC and then PT within SOC based on overall patients.

The incidence of TEAEs will be summarized with frequencies and percentages for patients in Safety Set (including number of TEAEs occurring, as well as rate of events [number of events /

100 years of exposure in each part]), by part and treatment group and also overall for Dasiglucagon group for the following:

- SOC and PT
- SOC, PT, and severity
- SOC, PT, and relationship to study drug
- SAEs by SOC and PT

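### Adverse events with an unknown start day are moved from open-label Part 2 into Part 1, about half of the moved events into the placebo column

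*SAP*

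**What the plan says.** SAP 6.1.8 covers AE and medication dates together: "If partial medication/AE dates occur, the convention for replacing missing dates for the purposes of calculating derived variables is as follows". For a start date with only the day missing, it states "If the month and year match the month and year of the first dose date, then impute as the day of the first dose date". There is one exception: "If this produces a date after the medication end date, assign 01". In any other month the day is set to the 1st. If the month is also missing and the year matches, the first-dose date is again used, subject to a similar end-date condition.

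SAP 9.1 fixes attribution: "An AE will be assigned to the treatment period the AE started". SAP section 9 tabulates safety by treatment received within period and part, and also for all dasiglucagon exposure pooled. SAP 9.1 adds event rates per 100 years of exposure.

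Day 1 falls in the first blinded period (SAP 6.1.7: "Part 1 – Treatment period 1: First 48-hours treatment period"). SAP 3.5 says of the sequences: "For Part 1, patients will be randomly assigned 1:1 in a double-blind fashion to 1 of 2 sequences". One of the two is "Placebo for dasiglucagon for 48 hours, followed by dasiglucagon 4 mg/mL for 48 hours". SAP section 3 then adds the open-label part: "After Part 1, patients will continue in open-label Part 2 to receive dasiglucagon for 21 days".

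**The concern.** Setting a partial start date to the first-dose day is a sound convention for deciding whether an event is treatment-emergent, because it errs toward counting it. In a single-treatment trial that is all it decides. Here the same date also decides which treatment the event is charged to, and Day 1 is a placebo day for half of the patients.

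Each patient has 2 placebo days out of 25 on treatment, so an undated event most probably began on dasiglucagon. The rule ignores this and sends the event to the start of Part 1. No other SAP rule uses the Part 2 start, the reporting visit or the form to keep the event in Part 2. What is at stake is the accuracy of the placebo and Part 2 columns in the AE tables. Treatment-emergent status and the primary endpoint are not affected.

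**Working it through.** The documents give no figure on this point to reproduce, so the two rules are applied directly.

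**Inputs.** Days 1–2 are period 1, Days 3–4 period 2 and Days 5–25 Part 2 (SAP 3.5, 6.1.7 and section 3). Sequences are 1:1 (SAP 3.5). Assumptions, not in the documents: first-dose dates are uniform over the calendar, and onset is uniform over the days considered.

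**Step 1: does the exception help?** It applies only if the imputed date falls after the end date. An event that began in Part 2 ends after Day 1, so it never applies to such an event.

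**Step 2: hand check in a 30-day month.** With the first dose on day k, study day d falls on calendar day k + d − 1. The number of Part 2 days in the first-dose month is min(21, max(0, 27 − k)).

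- k = 1 to 6: 21 each, total 6 × 21 = 126
- k = 7 to 26: 20 + 19 + … + 1 = 210
- k = 27 to 30: 0

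The total is 336 of 30 × 21 = 630, or 53.3%. All of these are imputed to Day 1.

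Events in the next month go to the 1st, which is study day 32 − k. For k = 28, 29 and 30 that is Day 4, 3 and 2, all in Part 1. This adds 3 × 21 = 63 events (10.0%).

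Moved out of Part 2: (336 + 63)/630 = 63.3%. Half of them, 31.7%, go to placebo under 1:1 sequences.

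**Step 3: full enumeration** over every first-dose date in four calendar years and both sequences, for Part 2 events with unknown start day:

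| Where the event is counted | Share |
|---|---|
| Placebo | 31.9% |
| Part 1 dasiglucagon | 31.9% |
| Part 2 (correct) | 36.1% |

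The first-dose month holds 54.0% of these events. All of those leave Part 2, half to each Part 1 column.

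**Step 4: all treatment days.** With onset uniform over Days 1–25, 35% of events with unknown day are counted as placebo, against 2/25 = 8% of treatment time.

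**Step 5: effect on rates,** at 12 patients with full planned exposure:

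- Placebo, and likewise Part 1 dasiglucagon: 12 × 2/365.25 = 0.066 patient-years; one event adds about 1,520 per 100 years.
- Pooled dasiglucagon: 12 × 23/365.25 = 0.756 patient-years; one event is about 132 per 100 years.

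A misplaced event therefore weighs equally in either Part 1 column, and far more there than in the pooled column it left.

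**The case against.** **Direction.** A reader might infer that the rule biases the safety comparison in favour of the drug generally. The documents do not support that. Of the displaced events, as many go to Part 1 dasiglucagon as to placebo, and the two columns have the same planned exposure. The expected difference between them is unchanged by these events, and their ratio is pulled toward 1. The pro-drug shift arises only against Part 2 or pooled dasiglucagon, a comparison that is not randomized and not formally tested. Nor does every displacement help the drug. AEs are collected from consent (Protocol 12.2), so an undated screening event in the first-dose month becomes a Day 1 dasiglucagon event in dasiglucagon-first patients. In the same patients, an undated period 2 placebo event in that month also moves to dasiglucagon. This objection stands and limits the claim about direction.

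**Frequency.** A reader might also take 64% as a share of all Part 2 events. It is a share of those with an unknown start day. Protocol 12.2 makes onset date and time a minimum AE item, entered within 5 days of awareness, and asks about AEs at every contact. The post-discharge diary is reviewed at each visit (Protocol 11.2.1.3). Undated events should be few, and there may be none. They are not excluded, though: the SAP provides for them, discharged patients rely on a paper diary kept by parents, and the Day 11 and Day 18 visits may be by telephone (Protocol 8.1).

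**Link between the rules.** SAP 9.1 does not say that the imputed date is used for period assignment. That is an inference, but the natural one: the convention names AE dates, serves derived variables, and is the only start date the SAP provides for such an event.

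**Rate inflation.** The figure of 1,520 per 100 years reflects the short placebo denominator and would apply equally to one genuine placebo event. It shows how sensitive the column is, and says nothing of how often the rule acts.

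**Conclusion.** The point holds as a minor but real error in the descriptive safety tables. Followed as written, and taking the imputed date to drive period assignment, the SAP always moves an undated Part 2 event in the first-dose month into Part 1. Under uniform onset over Days 5–25 and uniform first-dose dates, about 64% of Part 2 events with unknown day are misplaced: about 32% to placebo and about 32% to Part 1 dasiglucagon, which is the right drug but the wrong part.

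The share depends heavily on the first-dose day. In a 30-day month all Part 2 days fall in the first-dose month for first doses on days 1–6, 12 of 21 for day 15, and none from day 27 on.

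The placebo versus Part 1 dasiglucagon contrast is diluted but not biased in expectation by these events. Placebo against Part 2 or pooled dasiglucagon, including the exposure-adjusted rates, is shifted in the drug's favour. The absolute effect cannot be stated, because the number of undated events is unknown and probably small.

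**What to change.** In SAP 6.1.8, limit the first-dose imputation of AE start dates to the treatment-emergent flag. In SAP 9.1, add a separate attribution rule for treatment-emergent AEs with a partial start date:

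- Use the known date parts, the end date, and the visit or contact at which the event was first reported.
- Assign to Part 2 an event first reported in Part 2 as new since the previous contact.
- If the period is still unclear, count the event under dasiglucagon: in Part 2 if the known date parts allow it, otherwise in the patient's Part 1 dasiglucagon period.
- Flag every such event in the listing.

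The cost is a few sentences in the SAP and a small programming change. No new data are needed, since Protocol 12.2 already requires the date and time at which the investigator first learned of each AE. The downside is that dasiglucagon AE counts may look slightly less favourable. Making the change before unblinding avoids a later choice that could appear to be driven by the results.
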